11 ANALYSIS POPULATIONS

The main population for analysis will be the Compliant Exposure Set.

11.1 Enrolled Participant Set

The Enrolled Participant Set will consist of all enrolled participants who signed the ICF.

11.2 Compliant Exposure Set

The Compliant Exposure Set will consist of all enrolled participants who signed the ICF and who participated in either a Non-Exposure Event or an Exposure Event, have provided two urine samples (one urine sample prior to the event and one sample after a minimum 2h of participation in the Event) and are compliant with the Event Exposure Groups (Non-Exposure or Passive Exposure).

11.3 Active Exposure Set

The Active Exposure Set will consist of all enrolled participants who signed the ICF and who participated as IQOS Active Users in an Exposure Event, have provided two urine samples (one urine sample prior to the start of the event and one sample after a minimum of 2h after the start of the Active Exposure) and were compliant with the Active Exposure Group.

11.4 Protocol Deviations

All protocol deviations will be entered into the Clinical Trial Management System (CTMS) or other approved format.

Information from the source documents will represent the primary source of protocol deviations. Information following manual reviews after the event will be documented in follow-up letters, audit documentation and will be recorded and tracked in the CTMS or other approved format. Telecommunications and other verbal communications regarding deviations will be considered and handled as important communication, and documented and tracked as protocol deviations, as necessary.

Individual entries for protocol deviations that are recorded in the CTMS, or other approved format, following site monitoring and other manual reviews will be reviewed against the individual data points in the Case Report Form (CRF) database but will not be formally reconciled with the CRF database (e.g., their description or occurrence date). The overall procedures for managing protocol

deviations are described in the SOPs of the CRO Data Management Team. All deviations will be reviewed periodically, as determined at study start, to identify trends to improve monitoring and/or potential impact on the statistical analysis.

11.4.1 Major Protocol Deviations

Major protocol deviations are protocol deviations that may significantly impact the completeness, accuracy, and/or reliability of the study data or that may significantly affect a participant's rights, safety, or well-being.

11.4.2 Minor Protocol Deviations

Minor protocol deviations are defined as deviation that does not impact any of the following: (1) the safety of a subject participating the study; (2) the integrity of the data collected for the evaluation of the study; or (3) the overall evaluation and/or interpretation of the outcome of the study, specifically with respect to the primary objective(s).

12 PLANNED STATISTICAL ANALYSIS

12.1 General Considerations

The statistical evaluation will be performed using SAS[®], version 9.2 or later.

12.1.1 Stratified Presentation

For the primary analysis, the following stratification criteria will be used:

1. Product Use Status.
2. Event Type.
3. Sex.

12.1.2 Descriptive Statistics

Descriptive statistics for continuous variables will include the number of participants, number and percent of participants with missing data, the mean and standard deviation, geometric means and CV (for log-transformed variables), median, first and third quartiles, minimum and maximum, and 95% confidence interval (CI) for each product exposure, and summary across all participants.

12.1.3 Definitions for Statistical Data Analysis

12.1.3.1 Categorical Variables

Categorical variables used in this study are shown in [Table 5](#) below.

**Table 5. Categorical Variables Definitions**

Variable	Categories
Sex	Male Female
Event Type	Exposure Event Non-Exposure Event
Product Use Status	IQOS Active User IQOS Passive User Non-Smoker Cigarette Smoker

12.1.4 Handling of Dropouts or Missing Data (Including Outside the Limits of Quantification)

For BoExp parameters and creatinine:

- Values below the lower limit of quantification (LLOQ) will be imputed using LLOQ/2. For values above the upper limit of quantification (ULOQ), the value will be imputed using the ULOQ.
- The number of values below LLOQ or above ULOQ will be presented in each summary table.

The number of values below LLOQ or above ULOQ will be presented in each summary table, as well as the statistics on the other quantitative values.

However, if 50% or more data are below LLOQ or above ULOQ, only the number (%) of values below LLOQ or above ULOQ will be reported in the summaries, together with minimum (if no value below LLOQ is present) and maximum (if no value above ULOQ are present) of the observed values, and no other statistics will be reported.

For calculation of parameters derived as a ratio of two components (creatinine-adjusted endpoints) if the denominator is below LLOQ then the ratio will not be calculated and will be tabulated as “Not Calculated” in descriptive summaries and excluded from the main analysis. A sensitivity analysis will be produced by including derived values using LLOQ/2 values for the denominator of the impacted endpoint for the Compliant Exposure Set and Active Exposure Set.

For Duration of Exposure:

If the collection time of a urine sample is missing and the duration of exposure cannot be calculated, and therefore 2 hours of participation cannot be confirmed, the participant’s samples will not be analyzed and they will be excluded from the analysis set. These participants may be included in other descriptive analyses.

Participants enrolled in the study who did not participate for at least 2 hours of the planned Event (discontinued subjects), they will be included in data summaries for demographics, disposition, and self-reported questionnaires using the Enrolled Participant Set.

For participants with missing CASI data, they will be analyzed in the Study Population(s) when data are available, without imputation of the missing data.

12.2 Disposition of Participants

The disposition of participants will be listed and summarized.

12.3 Demographic and Other Baseline Characteristics

Demographic data collected from CASI will be summarized for each Study Population by event type (Exposure vs. Non-Exposure), product use status and sex.

12.4 Extent of Exposure (Product Consumption)

The number of *HeatSticks* used for each IQOS Active User will be listed by event. Summary statistics of *HeatSticks* usage will be presented by hour and over the entire event. IQOS exposure will also be presented as total per hour, total for the event, and average usage per hour for each Exposure Event and across all Exposure Events.

12.5 Food and Alcohol Consumption

The overall amount of food and alcohol consumed will be summarized by food and beverage type for each event.

12.6 Planned Statistical Analyses

12.6.1 Primary Analysis

12.6.1.1 Statistical Analysis of Primary Endpoints

For each urinary BoExp in the primary analysis NEQ, Total NNAL, Total NNN, the change between pre-event and end of study levels adjusted for creatinine will be modeled using a linear model in the Compliant Exposure Set.

The SAS procedure PROC MIXED will be used with the restricted maximum likelihood method for estimation of the parameters. The mixed model will have the change from baseline as dependent variable and the following covariates will be included in the model: Baseline, Sex, Event Type (Exposure or Non-Exposure), Duration of Exposure, Product Use Status, Product Use Status by Event Type interaction for all BoExp. In addition, an air quality covariate related to each BoExp is included in the model depending on the endpoint and is described in Appendix 15.2. This table also specifies the various IAQ covariates that are assessed using a step-wise regression approach for each BoExp. The algorithm is described below,

1. Fit a full model with all covariates

2. Drop one IAQ covariate and re-fit the model.
3. Perform a likelihood ratio test and drop the IAQ covariate with the largest p-value for the likelihood ratio statistic if it is more than 0.05.
4. Repeat steps 2 and 3 until no more IAQ covariates can be dropped.
5. Refit the final model with the IAQ covariates remaining in the model and estimate exposures for each product use group.

Appropriate contrasts will be constructed to determine the effect of passive exposure to IQOS aerosol during the Exposure Event on the mean change in levels of urinary BoExp together with the 95% CIs for non-smokers during an Exposure Event. Other contrasts can be constructed to determine the change in urinary BoExp for participants with other smoking status (Cigarette Smoker and IQOS Passive Users) after passive exposure to IQOS usage.

An example of SAS code for the final model is provided below,

```
Proc mixed data=_data_ method=reml;
Class event_type sex product_use;
Model endpoint = baseline sex event_type product_use event_type*product_use
duration <IAQ covariates> / ddfm=kr;
estimate 'Cigarette Smoker' intercept 1 baseline xx sex .5 .5 product_use 1 0 0
event type 1 event_type*product_use 1 0 0 0 0 duration xx IAQ1 xx ... IAQn xx /
alpha=0.05 cl;
Run;
```

We define xx are the mean of a continuous covariate for participants in the product use group across all Exposure Events. For air quality covariates, they will be the mean calculated over all Exposure Events since they were the same regardless of product use group.

The LSmeans and corresponding confidence intervals will be exponentiated, back-transformed to the original scale and reported as geometric means with its confidence intervals.

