8.2.1 Primary and Secondary Analysis of Urinary Biomarkers of Exposure

- Carbonyls: Acetaldehyde, Acrolein, Crotonaldehyde and Formaldehyde
 - At each event there are 3 machines where each collects 1 sample at 1 hour intervals over a 3 hour period.
 - All readings will be averaged over the 3 hour interval of an event and taken as one observation for all participants of the particular event.
- ISO measurement standards for ETS: 3-Ethenylpyridine (3-EP)
 - At each event there are 3 machines where each collects 2 samples at 3 hour intervals.
 - All readings from the 3 machines will be averaged and taken as one observation for all participants of the particular event.
- Real-time measurements of PM2.5 and PM10 suspended particles in air.
 - At each event there are 2 dedicated sensors measuring suspended particulate matter with a 1 minute interval monitoring.
 - For passively exposed participants we define the start time of exposure as the time of entry to the event room and end time of exposure as the time of collection of last urine sample. The exposure duration is defined as the start to end time of exposure for a participant. For each type of particulate matter (PM2.5 and PM10), the reading associated with a particular participant will be the average of all the readings from the 2 sensors depending on the participant's exposure duration.
 - For actively exposed participants we define the start time of exposure as the start time of first IQOS use and end time of exposure as the time of collection of last urine sample. The exposure duration is defined as the start to end time of exposure for a participant. For each type of particulate matter (PM2.5 and PM10), the reading associated with a particular participant will be the average of all the readings from the 2 sensors depending on the participant's exposure duration.

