8.2.2 Secondary Analysis of Indoor Air Quality Measurements

- Carbonyls: Acetaldehyde, Acrolein, Crotonaldehyde and Formaldehyde
 - At each event there are 3 suitcases sampling each sample at 1 hour intervals over 3 hours.
 - Each of the 9 observations will be used as the observations for the associated event.
- ISO measurement standards for ETS: 3-Ethenylpyridine (3-EP) and Nicotine
 - At each event there are 3 suitcases sampling 2 replicate samples at the end of the 3 hour interval.
 - Each of the 6 observations will be used as the observations for the associated event.
- Tobacco Specific Nitrosamines: NNN and NNK
 - At each event there are 3 suitcases sampling 2 replicate samples at the end of the 3 hour interval.
 - Each of the 6 observations will be used as the observations for the associated event.

- Real-time measurements of PM2.5 and PM10 suspended particles in air.
 - At each event there are 2 sensors measuring the suspended particulate matter a 1 minute interval monitoring.
 - For each sensors, the average of all readings will be calculated from the start till end of the event. These averages will be used as observations for that particular event.

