12.6.2.1.1 Carbonyls

During each Exposure and Non-Exposure Event, there are 3 sampling cases that collects air for the assessment of carbonyls at 1 hour intervals. Each sampling case was placed at the same location during an Event.

The SAS procedure PROC MIXED will be used with the restricted maximum likelihood method for estimation of the parameters. The mixed model will have the carbonyl reading as dependent variable and the following covariates will be included in the model: Location, Event Number (Exposure Events 1-4 and Non-Exposure Event 1 and 2) and Event Type (Exposure and Non-Exposure Event). A repeated statement will be used to model repeated measures for the time variable.

The denominator degrees of freedom will be determined using the method of Kenward and Roger (1997). In case of non-convergence of the preferred model or memory space issues, the Kenward-Roger method will be replaced by Satterthwaite approximation.

The SAS code for the mixed model to be used is shown below:

```
Proc mixed data=_data_ method=reml;
Class location time event_type;
Model endpoint = location event type event num/ ddfm=kr;
Repeated time/subject=location(event num) type=cs;
Lsmeans event_type / diff alpha=0.05 cl;
Lsmeans location / diff alpha=0.05 cl;
Run;
```

The Geometric LS means and estimate of the ratio of geometric means between Exposure and Non-Exposure Events along with its 95% CI will be presented in tables for Formaldehyde, Acetaldehyde, Acrolein and Crotonaldehyde. The geometric LS means and ratio of geometric means together with their respective CIs are calculated by exponentiating the LSmeans and differences between exposures groups.

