15.2 Covariates used in Analysis of Urinary BoExp

Table 8. Covariates for Analysis of Urinary BoExp

Endpoint	Included Covariates ¹	Included Air Quality Covariates ¹	Evaluated Air Quality Covariates
NEQ	Baseline, Sex, Event Type, Duration of Exposure, Product Use Status, Product Use Status by Event Type	Nicotine	Formaldehyde, Acetaldehyde, Acrolein, Crotonaldehyde, 3-ethenylpyridine, PM2.5, and PM10
Total NNAL	Baseline, Sex, Event Type, Duration of Exposure, Product Use Status, Product Use Status by Event Type	NNK	Formaldehyde, Acetaldehyde, Acrolein, Crotonaldehyde, 3-ethenylpyridine, PM2.5, and PM10
Total NNN	Baseline, Sex, Event Type, Duration of Exposure, Product Use Status, Product Use Status by Event Type	NNN	Formaldehyde, Acetaldehyde, Acrolein, Crotonaldehyde, 3-ethenylpyridine, PM2.5, and PM10
HMPMA	Baseline, Sex, Event Type, Duration of Exposure, Product Use Status, Product Use Status by Event Type	Crotonaldehyde	Formaldehyde, Acetaldehyde, Acrolein, 3-ethenylpyridine, PM2.5, and PM10
3-HPMA	Baseline, Sex, Event Type, Duration of Exposure, Product Use Status, Product Use Status by Event Type	Acrolein	Formaldehyde, Acetaldehyde, Crotonaldehyde, 3-ethenylpyridine, PM2.5, and PM10

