**Table 8. Covariates for Analysis of Urinary BoExp**

Endpoint	Included Covariates ¹	Included Air Quality Covariates ¹	Evaluated Air Quality Covariates
S-PMA	Baseline, Sex, Event Type, Duration of Exposure, Product Use Status, Product Use Status by Event Type	NNK	Formaldehyde, Acetaldehyde, Acrolein, Crotonaldehyde, 3-ethenylpyridine, PM2.5, and PM10
HEMA	Baseline, Sex, Event Type, Duration of Exposure, Product Use Status, Product Use Status by Event Type	NNK	Formaldehyde, Acetaldehyde, Acrolein, Crotonaldehyde, 3-ethenylpyridine, PM2.5, and PM10

1 These covariates will be included in the statistical models for their respective urinary BoExp

2 The covariates pertaining to air quality will be assessed as described in Section 12.6.1.1

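### Backward selection of air-quality covariates in the primary BoExp model starts from a rank-deficient model, so the elimination rule does not fix the final covariate set unless enough event-level air columns are constant

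*SAP*

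**What the plan says.** SAP 12.6.1.1 models the change in each creatinine-adjusted biomarker on baseline, sex, event type, duration, product use status, the product use by event type interaction, one forced air marker, and a set of further air covariates chosen by backward elimination. The rule fits everything, tests each air covariate by removing it, and then: "Perform a likelihood ratio test and drop the IAQ covariate with the largest p-value", provided that p-value exceeds 0.05. It repeats until nothing more can go.

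Table 8 (SAP 15.2) lists the evaluated covariates for the three co-primary biomarkers: "Formaldehyde, Acetaldehyde, Acrolein, Crotonaldehyde, 3-ethenylpyridine, PM2.5, and PM10". The forced markers are nicotine for NEQ, NNK for Total NNAL and NNN for Total NNN. A footnote extends the rule to every biomarker in the table: "The covariates pertaining to air quality will be assessed as described in Section 12.6.1.1". SAP 12.6.2.3 repeats the algorithm in the Active Exposure Set.

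SAP 8.2.1 averages each carbonyl and 3-EP within the event, and the average is "taken as one observation for all participants of the particular event". Only PM2.5 and PM10 are built from each participant's own time in the room. SAP 12.6.2.1.1 numbers the events: "Exposure Events 1-4 and Non-Exposure Event 1 and 2". I found no rule in 12.6.1.1, Table 8 or section 14 for ties, aliased terms or a limit on event-level covariates.

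**The concern.** A covariate with one value per event carries only as many independent pieces of information as there are events, however many participants attend. If the starting model holds more such columns than events, some are exact linear combinations of the others. Removing one of those leaves the fit unchanged, so there is nothing to test, and a rule based on the largest p-value cannot choose among them. The final covariate set would then depend on column order or on a programmer's convention.

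These are the models for the co-primary endpoints. The selected sets also carry into the post hoc HeatStick analysis of SAP 14.5.1. SAP 14.1 describes interest in linking air compounds with urinary biomarkers, and coefficients that depend on an arbitrary elimination order cannot support that reading.

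**Working it through.** **Inputs**
- Events: 6, of which 4 are Exposure and 2 Non-Exposure (SAP 12.6.2.1.1). Protocol Table 5 planned 5 (2 Non-Exposure, 3 Exposure), used below as a range check.
- Event-level evaluated covariates: four carbonyls and 3-EP (SAP 8.2.1, Table 8). PM2.5 and PM10 vary within an event and are not counted.
- Forced marker: taken as event-level by inference. SAP 8.2.1 gives no derivation for nicotine, NNK or NNN. But SAP 8.2.2 has only per-event samples for them ("Each of the 6 observations will be used as the observations for the associated event"), and 12.6.1.1 says of air covariates that "they will be the mean calculated over all Exposure Events since they were the same regardless of product use group".

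**Step 1: count columns.** Let c be the number of event-level columns and E the number of events. The rank is at most min(c, E), so at least c − E columns are redundant.

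| Model | c | E | Maximum rank | Redundant |
|---|---|---|---|---|
| NEQ, Total NNAL, Total NNN (also S-PMA, HEMA) | 1 intercept + 1 event type + 1 forced + 5 = 8 | 6 | 6 | 2 |
| HMPMA, 3-HPMA | 1 + 1 + 1 + 4 = 7 | 6 | 6 | 1 |
| Active set, forced marker not a carbonyl | 1 + 1 + 5 = 7 | 4 | 4 | 3 |
| Active set, HMPMA and 3-HPMA | 1 + 1 + 4 = 6 | 4 | 4 | 2 |

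The participant-level columns are baseline 1, sex 1, product use 2, interaction 2, duration 1 and PM 2, total 9. The full primary model therefore has 8 + 9 = 17 columns and rank 6 + 9 = 15. For HMPMA and 3-HPMA it is 16 columns and rank 15. With five events the primary model has rank 5 + 9 = 14 of 17. Numerical checks of the rank agree.

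**Step 2: apply the rule to the primary model.** The test df is rank(full) − rank(reduced).
- Drop any one of the five evaluated event-level terms: 15 − 15 = 0 df. The maximum-likelihood (ML) likelihood ratio is 0.000.
- Drop PM2.5 or PM10: 15 − 14 = 1 df, a proper test.
- After one event-level term has gone, the other four again have 0 df. After two, 6 columns remain with rank 6 and every drop has 1 df.

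That is a five-way tie followed by a four-way tie: 5 × 4 = 20 ordered paths, or 20 / 2 = 10 different pairs removed. If a 0-df test is read as p = 1, the choice within the tie is arbitrary. If it is read as missing, only the PM terms can be ranked and the redundant terms are never removed.

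**Step 3: the exception.** A column that is constant across events, for example all below quantification and set to one value, duplicates the intercept. With one constant among the six air columns, 7 columns are left on 6 events and one tied elimination remains. With two, 6 columns are left and the ties among varying terms vanish. For HMPMA and 3-HPMA one constant among five is enough (7 − 1 = 6).

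**Step 4: carry-over to SAP 14.5.1.** Adding the event total of HeatSticks to k event-level air terms gives 2 + 1 + k columns. The HeatStick coefficient is identified only if 3 + k ≤ 6, so k ≤ 3. With k = 4 there are 7 columns at rank 6. With the forced marker alone there are 4 columns at rank 4.

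**Step 5: size, as illustration.** All inputs here are assumed: air covariates unrelated to the outcome, event-level SD 0.3 on the log scale, ML tests at 0.05, 150 to 250 data sets per setting.
- Different tie-breaks gave different final sets in 13–24% of data sets with no between-event variation, 48–63% with a between-event SD of 0.1 log units, and 78–91% with 0.2.
- Spread over tie-breaks of the Non-Smoker Exposure Event estimate and of the 14.1 contrast: equal event sizes, median at most 0.004 and 95th percentile at most 0.017 log units; Exposure Event sizes 4:3:2:1, median at most 0.027 and 95th percentile at most 0.071. The standard errors were about 0.066 and 0.093.

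**The case against.** The strongest reply is that the reported results hardly depend on the choice. The SAP tests no hypothesis (6.3.1), reports geometric means at average covariate values rather than air coefficients, and plans no separate reading of those coefficients. This stands, and it limits the point to reproducibility and interpretation.

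The constant-column exception is also not remote. Protocol 2.1.1 reports an earlier indoor-air study in which nicotine and acetaldehyde were the only harmful constituents detected after IQOS use. If NNK or NNN and also 3-EP were constant across events, every tie for Total NNAL or Total NNN would vanish. This stands as a condition. Restaurant carbonyls may still vary, and for NEQ, if nicotine varies, two of the five evaluated terms would have to be constant. The higher instability percentages also need between-event variation that the SAP model leaves out; without it the figure is 13–24%.

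Four stronger readings are tempting, and the documents do not support them.
- *The model cannot run.* SAP 14.1 shows that primary results were obtained, and 14.4 records non-convergence only for an air-quality model.
- *The likelihood ratio tests are invalid because they use REML.* The SAP names REML "with the restricted maximum likelihood method for estimation of the parameters" and in code labelled as the final model. It does not say which likelihood step 3 uses, so ML there would not contradict it.
- *The HeatStick analysis of 14.5.1 fails.* With four or more event-level air terms its coefficient is not identified, but that section reports means and Exposure to Non-Exposure ratios. At group averages that contrast remained estimable when checked.
- *The SAP is at fault for not reporting the order used.* SAP sections 3 and 13.3 send changes and added analyses to the study report, which is not available here. The fault is the missing rule.

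**Conclusion.** The point holds in limited form. The selection rule for the co-primary models cannot be carried out as written when the event-level air means vary freely: two event-level eliminations are undetermined for NEQ, Total NNAL and Total NNN, and one for HMPMA and 3-HPMA. In the Active set the starting model exceeds its four events by three or two columns.

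The column count comes from the documents, except that the event-level status of the nicotine, NNK and NNN markers is inferred. The ties require fewer than two constant columns among six (none among five for HMPMA and 3-HPMA).

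A reader might infer that the primary estimate is unreliable. The evidence does not show that: the illustrative 95th percentile is about 0.02 log units with equal event sizes (exp(0.02) = 1.02, about 2%) and up to 0.07 with unequal sizes (exp(0.07) = 1.07, about 7%), on assumed inputs. What is lost is a reproducible final model and any separate meaning for the IAQ and event-type coefficients, and for the HeatStick coefficient when four or more event-level air terms remain. It should be fixed, but it does not overturn the reported means.

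**What to change.** Keep the reported model. Then:

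1. Add to SAP section 14, labelled post hoc and shown beside the selected model, a BoExp model with only the forced Table 8 marker and no stepwise selection. It has 3 event-level columns on 6 events. Do the same in the Active set (intercept and marker, 2 columns on 4 events). If the marker is constant across events, use the model without air covariates.
2. Add a one-marker version of 14.5.1 alongside the specified one (4 event-level columns, rank 4).
3. State in SAP 8.2.1 that the nicotine, NNK or NNN covariate is the event mean.
4. For the selection already run, record the elimination order, how 0-df terms were handled and which likelihood was used. Models with different fixed effects should be compared by ML.
5. State that IAQ and event-type coefficients are not interpreted separately.

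The cost is one extra table, one derivation line and a record of what was run; no result is removed. The one-marker model stays within Protocol 12.4, which lists IAQ as a fixed effect. A model without air covariates departs from it and should be labelled so. The one-marker estimate can differ somewhat from the selected one: the simulated 95th percentile was 0.030 log units with equal event sizes and 0.104 with sizes 4:3:2:1. That is why both should be shown.

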10 CHANGES FROM THE PROTOCOL SPECIFIED STATISTICAL ANALYSES

For the primary and secondary analysis, the random subject effect is removed as there are no repeated measures.

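### The primary model names REML and then selects fixed air-quality covariates by likelihood ratio test with no switch to ML, so the 0.05 rule does not mean what it says

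*SAP*

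**What the plan says.** SAP 12.6.1.1 states: "The SAS procedure PROC MIXED will be used with the restricted maximum likelihood method for estimation of the parameters". It then gives a five-step backward algorithm. Fit all covariates, drop one IAQ covariate and refit, then "Perform a likelihood ratio test and drop the IAQ covariate with the largest p-value for the likelihood ratio statistic" "if it is more than 0.05". Repeat until nothing more can be dropped, then refit the final model and estimate.

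The only code is introduced by "An example of SAS code for the final model is provided below" and begins "Proc mixed data=_data_ method=reml". The selection fits have no code of their own, and nothing in the section mentions ML.

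Other relevant places:
- Section 10: "the random subject effect is removed as there are no repeated measures". The primary model is therefore an ordinary linear model.
- Appendix 15.2 (Table 8): for NEQ, Total NNAL and Total NNN the tested candidates are "Formaldehyde, Acetaldehyde, Acrolein, Crotonaldehyde, 3-ethenylpyridine, PM2.5, and PM10". One further air marker is always included.
- Section 8.2.1: the carbonyl and 3-EP values are averaged and "taken as one observation for all participants of the particular event". PM2.5 and PM10 are averaged over each participant's own stay.
- Section 6.2: µg/m³ is given for every air marker except PM, which has no unit.
- Section 12.6.2.1.4: IAQ values are natural-log transformed before analysis, except PM. This stands under the descriptive IAQ analysis and is not repeated where IAQ values serve as covariates.
- Section 12.6.2.2 models the secondary biomarkers in the same way as the primary ones, and 12.6.2.3 repeats the selection rule for the Active Exposure Set.

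**The concern.** A likelihood ratio test of a fixed effect needs two likelihoods for the same data. REML maximises the likelihood of contrasts that are free of the fixed effects, and those contrasts change when a column leaves the design matrix. The difference between two such REML fits is not a chi-square statistic, and it can be negative.

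A programmer who follows 12.6.1.1 literally would therefore apply a cut-off that is not a 5% test. Two people who enter the same marker on different scales could keep different covariates. Where several statistics are negative, all have p = 1 and the instruction to drop the one with the largest p-value is undefined.

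The rule sets the final model for all three co-primary biomarkers and the four secondary ones, and a separate model in the Active Exposure Set. Sections 14.1 and 14.5.1 build on the Compliant Exposure Set models.

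**Working it through.** The plan gives no figure to reproduce: 0.05 is a rule, and Section 9 gives no SD or effect size.

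**Formulas.** For a linear model with n observations, p columns and residual sum of squares RSS:
- −2 log ML = n ln(2π RSS/n) + n
- −2 log REML = (n − p) ln(2π RSS/(n − p)) + (n − p) + ln|X′X|

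Let SSx be the residual sum of squares of the dropped covariate x given the other terms. Removing x lowers ln|X′X| by ln(SSx). Since SE² = s²/SSx, the REML difference is approximately

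t² + ln(2π SE²).

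The first term is the evidence and the second is scale. The scale term vanishes only at SE = 1/√(2π) = 0.399. Multiplying x by 1000 divides SE by 1000 and moves the statistic by −2 ln(1000) = −13.8, against a critical value of 3.84.

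**Inputs.** From the documents: 169 + 169 = 338 observations, 4 Exposure and 2 Non-Exposure Events (SAP 12.6.2.1.1), a 50/25/25 product-use mix, and the fixed effects of 12.6.1.1. Assumed, because the documents are silent: residual SD 0.5 on the log scale, and one event-level candidate with geometric mean 20 and log-SD 0.3.

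**One simulated data set with no true effect:**

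| Scale of x | ML statistic | REML statistic | REML − ML | F-test p |
|---|---|---|---|---|
| raw, mg/m³ | 0.991 | 6.216 | +5.225 | 0.327 |
| raw, µg/m³ | 0.991 | −7.600 | −8.591 | 0.327 |
| raw, ng/m³ | 0.991 | −21.415 | −22.406 | 0.327 |
| ln, µg/m³ or ng/m³ | 1.452 | −1.001 | −2.453 | 0.236 |

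The approximation matched every REML value to three decimals. In raw µg/m³ the ML statistic would have to reach 3.84 + 8.59 = 12.43 (p about 0.0004) to be kept. On the log scale it would have to reach 3.84 + 2.45 = 6.29 (p about 0.012).

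**Retention over 4,000 data sets per setting:**

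| Scale | REML, no effect | REML, expected t = 2.8 | REML, expected t = 5 | REML statistic < 0, no effect |
|---|---|---|---|---|
| raw, mg/m³ | 99.5% | 100% | 100% | 0% |
| raw, µg/m³ | 0.0% | 25.3% | 93.0% | 99.6% |
| raw, ng/m³ | 0.0% | 1.3% | 43.4% | 100% |
| ln (any unit) | 1.5% | 63.8% | 99.2% | 82.7% |

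For comparison, ML keeps 5.2–5.3% with no effect and 80.8–81.7% at t = 2.8. The F-test keeps 4.8–4.9% and 79.6–80.6%. For a raw covariate neither changes with the unit. Repeat simulations gave 1.6% to about 2% for the logged null covariate. A covariate that varies between participants, as PM does, gave 99% (mg) and 0.15% (µg) null retention.

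**Effect on the reported estimate.** The primary model contains product use, event type and their interaction, so residuals sum to zero within each product-by-event cell. A fitted value at a cell's own covariate means therefore equals that cell's observed mean change, whichever IAQ covariates are kept. The SAP estimate departs from this in two ways: sex is set at 0.5/0.5, and IAQ is averaged over events, not over the cell's participants. In simulation, keeping versus dropping one event-level candidate moved the Non-Smoker Exposure estimate by 0.0016 log units with no effect (3% of its SE). With an effect of 0.02 log units per µg/m³ it moved by 0.006 (11% of its SE). The SE changed by about 2% or less. The Exposure versus Non-Exposure contrast described in 14.1 also moved by 3% and 11% of its SE.

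**The case against.** Four points on the other side carry weight.

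1. **REML for the test is inferred.** The code is labelled as being for the final model, and the closing refit step is compatible with ML selection followed by a REML refit. This stands as a caution. Still, REML is the only likelihood named, and a pre-specified rule should not depend on an unstated switch.

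2. **The log rule.** If 12.6.2.1.4 also governs the covariates, a unit change is absorbed by the intercept, and unit dependence remains only for PM2.5 and PM10. This stands. The test is then unit-free for the other candidates but still too strict.

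3. **The extreme figures are not planned.** A reader might infer that pure noise is almost always kept, or that selection follows the unit and ignores the evidence. The documents support neither. The SAP fixes µg/m³ for all markers except PM, and on the raw scale in that unit the error is towards keeping too few covariates. Evidence always enters through t²: at expected t = 5, 93% are kept in raw µg/m³.

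4. **Little effect on the result.** A reader might infer that the co-primary estimates are invalid. They are not: the estimate is taken at Exposure Event means and barely moves, and the SAP tests no formal hypothesis.

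The simulation also uses one candidate where the primary biomarkers have seven, so its percentages describe a single test and not the whole algorithm.

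**Conclusion.** The point holds, at moderate severity. As written, 12.6.1.1 and 12.6.2.3 compare REML fits with different fixed effects, and the 0.05 threshold is then not a 5% test. For logged covariates the rule is unit-free but keeps about 2% of null covariates instead of 5%. For untransformed ones, PM2.5 and PM10 at least, retention depends on the unit as well as on the evidence. Negative statistics leave the choice of covariate to drop undefined.

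The consequence lies in which IAQ covariates remain and in their coefficients, and much less in the Non-Smoker Exposure estimate or its SE. The percentages rest on the assumed residual SD and marker distribution. The 3% to 11% shift grows with the assumed effect and with the spread of marker levels between events, so it is an order of magnitude only. None of these figures carries over to the Active Exposure Set, where the numbers and SEs differ.

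The rank of the starting model is a separate matter. With six events and event type in the model, only 4 of the 6 event-level markers can be estimated (17 columns, rank 15). With the five events of Protocol Table 5 it is 3 of 6.

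**What to change.** In SAP 12.6.1.1 and 12.6.2.3, and by reference 12.6.2.2:
- Run the selection steps with method=ml, or use the Type 3 F-test of each IAQ term within a single fit. Without a random subject effect the F-test is exact under the model as specified.
- Refit only the final chosen model with method=reml.
- State the scale (raw or natural log) and the unit of every IAQ covariate, PM2.5 and PM10 included.
- If ML was in fact used for selection, say so.

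The text change is a few sentences and the program change is one option. The SAP shows that primary results had already been reviewed when the post-hoc sections were added. If REML was used, selection must therefore be rerun for the seven biomarkers in the Compliant Exposure Set and for the Active Exposure Set, and any change in the retained covariates reported. No new data are needed. This fix does not resolve the rank deficiency of the full starting model, which needs its own correction.
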